- 20. Potential subjects cannot have received opiates, including opiate-containing anti-cough agents, within 14 days prior to the screening period. Subjects are prohibited from using opioids, including naltrexone, for the duration of the study.
- 21. Potential subjects cannot currently be receiving benzodiazepines or other CNS Depressant Class Drugs that when used concomitantly with opioids are known to have the potential to cause added pharmacologic effects of depressing CNS activity (See Section 9.6.2.2 ("Benzodiazepines and Other CNS Depressant Class Drugs").
- 22. Potential subjects cannot currently be receiving medications that affect serotonergic neurotransmission and that when used concomitantly with opioids can cause serotonin syndrome (See Section 9.6.2.3 ("Serotonergic Class Drugs").
- 23. Alcohol consumption should be limited for the duration of study treatment (due to the potential cause of added pharmacologic effects of CNS depression when used concomitantly with opioids.
- 24. Change of IPF-related drug treatment regimen within 8 weeks of Screening.

Cardiac-related Exclusions:

- 25. Subjects with a history of congestive heart failure of Class 2 or higher as graded using the New York Heart Association classification (*Appendix 8*).
- 26. Subjects with a history of angina pectoris Grade 2 or higher as graded using the Canadian Cardiovascular Society grading scale (*Appendix 7*).
- 27. History of ventricular tachycardia, Torsade de Pointes, or family history of sudden death.
- 28. Myocardial infarction or acute coronary syndrome within the previous 3 months, as reported by the subject.
- 29. Serum potassium below the laboratory lower limit of normal.
- 30. QTcF interval >450 ms (mean of 3 screening ECG QTcF values) if QRS <120 ms (mean of 3 screening ECG QRS values); QTcF interval >480 ms in the presence of Right Bundle Branch Block (RBBB) and/or QRS ≥ 120 ms
- 31. Heart rate < 45 bpm on any screening measurement. Subjects with a resting heart rate of < 45 bpm will have it repeated once after 5 minutes in the supine position, and if it remains < 45 bpm during the repeat, they will be considered a screen failure.
- 32. Use of a medication having a "known risk" of Torsade de Pointes (categorized as "KR" on the Credible Meds[®] website) is not permitted at entry or during the study (See *Appendix 9*).

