9.2.3 Blinding and Randomization of Study Treatments

Randomization will be performed via IVRS/IWRS. Upon confirmation of eligibility by the study site and completion of all scheduled procedures at the Baseline (Day -1) visit, subjects will be randomized in a 1:1 ratio to either NAL ER tablets or placebo tablets for Treatment Period 1. Subjects will take the converse study treatment during Treatment Period 2 (the second crossover period).

9.3 **Procedure for Breaking the Randomization Code**

Under normal circumstances, the blind will not be broken. In the event of a medical emergency, when management of a subject's condition requires knowledge of the treatment assignment, the blind may be broken via the IVRS/IWRS.

Reasons for unblinding will be documented in the eCRF. The date and the identity of the person responsible for breaking the blind must be also documented.

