4.8 Medical History and Concomitant Illnesses

Medical history is assessed at screening and include prior and ongoing medical illnesses and conditions and prior surgical procedures not related to the primary diagnosis.

Medical history summaries will be based upon the Safety Set as defined in Section 4.5.

| Trevi Therapeutics, Inc. | | | |
|--------------------------|-------|------|---------------------------|
| TR12 | | | Statistical Analysis Plan |
| | •11 1 | 11 . | |

Medical History terms will be coded using Medical Dictionary for Regulatory Activities (MedDRA) version 22.0 or later version.

Medical History terms will be listed by subject.

4.9 **Prior and Concomitant Medications**

Any medication taken by a subject within the 14 days prior to the screening period, and during the course of the study, will be recorded on the eCRF along with the reason for use. During the study, each subject will be instructed to report the use of all medication, including over-the-counter (OTC) medications, herbal medications, vitamins, and nutritional supplements on the study specific medication log. After screening, prohibited or restricted medications are to be recorded on the corresponding Concomitant Medication eCRF.

Medications will be coded using the World Health Organization Drug Dictionary (WHODD), version global 2019 March B3 or later version and will be presented by Reported Term, WHODD Anatomical-Therapeutic-Chemical (ATC) therapeutic class IV and preferred term (PT).

- Medication start and stop dates will be compared to the dates of IMP intake in both Treatment Periods 1 and 2: Medications that start and stop prior to the date of first of IMP intake in Treatment Period 1 will be classified as prior;
- A therapy is concomitant to the NAL-ER if it started before the date of first NAL-ER intake and stopped on or after the date of first NAL-ER intake or if it started on or after the date of first NAL-ER intake and before the date of last NAL-ER intake.

A therapy is concomitant to the placebo if it started before the date of first placebo intake and stopped on or after the date of first placebo intake or if it started on or after the date of first NAL-ER intake and before the date of last placebo intake.If medication start and/or stop dates are missing or partial, the dates will be compared as far as possible with the date of first dose of study medication.

Prior and concomitant medications will be listed by subject as defined in SAP section 4.2.4.

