Concomitant medications summaries will be based upon the Safety Set as defined in Section 4.5.

Concomitant medications will be tabulated by Anatomical and Therapeutic Class (ATC) of World Health Organization (WHO) drug and preferred term, and as defined in SAP section 4.2.5. Of note: some medications may be concomitant to both treatment arms; these will be duplicated in the corresponding summary table.

Subgroup of patients with prior and concomitant use of anti-fibrotic therapies will be identified based on the review od study medical monitor. Efficacy summaries may be presented in the subgroup of patients with anti-fibrotic therapies as described in the relevant sections of this SAP.

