4.11.1.6 Examination of Subgroups

Primary endpoint summaries will be produced for gender and anti-fibrotic therapies (defined in section 4.9 of this SAP) subgroups.

As described in section 4.11.3, selected secondary endpoint summaries will be produced for gender and anti-fibrotic therapies subgroups.

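### The anti-fibrotic subgroup has no reference date, and its two defining terms cannot both fit one medication record, so it does not identify patients on background therapy at baseline

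*SAP*

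**What the plan says.** The subgroup is defined in SAP 4.9 (Prior and Concomitant Medications): "Subgroup of patients with prior and concomitant use of anti-fibrotic therapies will be identified based on the review od study medical monitor". SAP 4.11.1.6 adds nothing of its own and refers back: "Primary endpoint summaries will be produced for gender and anti-fibrotic therapies (defined in section 4.9 of this SAP) subgroups". SAP 4.11.2, 4.11.3.1 and 4.11.3.2 then call for subgroup summary tables and plots of daytime, 24-hour and nighttime cough frequency.

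SAP 4.9 also fixes the meaning of the two words that the definition uses.

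- *Prior*: "Medications that start and stop prior to the date of first of IMP intake in Treatment Period 1 will be classified as prior".
- *Concomitant to NAL ER*: either started before the first NAL ER intake and stopped on or after that date, or "if it started on or after the date of first NAL-ER intake and before the date of last NAL-ER intake".
- *Concomitant to placebo*: the same first branch for placebo, or "if it started on or after the date of first NAL-ER intake and before the date of last placebo intake".

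Medication records cover "Any medication taken by a subject within the 14 days prior to the screening period, and during the course of the study". Protocol 7.3, exclusion 24, removes patients with "Change of IPF-related drug treatment regimen within 8 weeks of Screening". Protocol 9.6.1 otherwise allows clinically indicated medication that is not prohibited. Protocol 9.6.2 to 9.6.2.4 do not name anti-fibrotics; the text of Appendix 9 was not available for this check.

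**The concern.** The natural question for this subgroup is whether the NAL ER effect on cough is also seen in patients already taking an anti-fibrotic. That needs membership fixed by use at baseline. The SAP gives no baseline date, uses two terms that it has defined in a way that does not describe a continuing user, and leaves the decision to a review with no stated criterion or cut-off.

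Two things follow. First, two programmers could build different subgroups from the same data, and one literal version admits patients on the strength of a drug first taken after randomisation. Second, in a crossover, a patient who starts or stops an anti-fibrotic between the two Day 22 recordings has a NAL ER minus placebo contrast that also contains the effect of that change, if the drug affects cough. Nothing in the subgroup outputs would show this.

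**Working it through.** The plan states no figure here, so there is none to reproduce. The check is to apply the SAP 4.9 date rules literally.

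**Study clock.** Protocol 9.2.3 places randomisation at the baseline visit: "completion of all scheduled procedures at the Baseline (Day -1) visit, subjects will be randomized in a 1:1 ratio". The first dose is taken on the evening of Day 1 and the last Period 1 dose on the morning of Day 22. Visit 6 (Day 36) normally doubles as Day -1 of Period 2, so Period 2 Day 1 is study Day 37 and its Day 22 is 37 + 21 = Day 58.

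**Can one record be both?** *Prior* requires a start and a stop before Day 1. The first *concomitant* branch requires a stop on or after the first intake of NAL ER or placebo, which is Day 1 or later. The second requires a start on or after the first NAL ER intake, again Day 1 or later. Each branch contradicts *prior*. A search over start days -60 to 74, every later stop day up to 75, and both arms found no record that was both.

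**Example records**

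| Anti-fibrotic record | Arm 1 (NAL ER, then placebo) | Arm 2 (placebo, then NAL ER) |
|---|---|---|
| Started before screening, ongoing | concomitant to both | concomitant to both |
| Started before screening, stopped Day -20 | prior only | prior only |
| Started Day 10, ongoing | concomitant to both | concomitant to NAL ER only |
| Started Day 30 (washout), ongoing | concomitant to placebo only | concomitant to NAL ER only |
| Started Day 45 (Period 2), ongoing | concomitant to placebo only | concomitant to NAL ER only |
| Started Day 10, stopped Day 20 | concomitant to both | neither |

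**Read as either category.** The first five rows are all in the subgroup. The continuing user is pooled with a patient untreated throughout dosing (row 2) and with patients who started after randomisation (rows 3 to 5).

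**Read as both categories.** A patient needs two separate records, one closed before dosing and another open or started later. The continuing user in row 1 has one record, which is concomitant only, and is left out.

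**A separate wording fault.** The last row is in the subgroup in Arm 1 and out of it in Arm 2. The cause is that the second branch of the placebo rule is anchored to first NAL ER intake, where first placebo intake seems to be meant. As written, the same drug history can be classed differently by randomised sequence.

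**The case against.** The strongest reply is that the phrase, in ordinary language, means use before the study that carried on into it, and that a medical monitor would apply it that way using coded drug names and dates. That may well be what was intended, so a reader should not infer that the subgroup certainly takes in drugs stopped before dosing. But the ordinary meaning is not the one SAP 4.9 gives these words, and a review without a criterion or cut-off does not settle which meaning applies. The ambiguity stands.

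The opportunity for harm is also narrow, and this limits the point. Exclusion 24 and the 14-day look-back make a recorded stop before screening unlikely, so a recorded pre-dose stop would fall mainly in the screening window of at most 45 days. Protocol 9.6.1 tells subjects to consult the investigator before taking anything new. Later changes are not barred, but they should be few.

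Other stronger readings are not supported:

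- A reader might infer that the SAP presents its members as patients on an unchanged regimen and then breaks that promise. It makes no such promise; it never calls this a baseline or unchanged-use subgroup.
- A reader might infer that members are picked with knowledge of treatment. SAP 4.9 is silent on the blinding of this review, but Protocol 6.4 keeps sponsor and CRO clinical staff blinded.
- A reader might put a misclassification percentage on it. The documents give no count of users or of changes, and recruitment ended before the planned total. Counting every starter and stopper would also overstate it: a baseline user who stops after dosing begins is a member under the either-category reading and under a baseline rule alike.

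**Conclusion.** The definition is faulty as written and worth correcting, but the matter is minor. Under the section's own terms, neither reading selects patients on background anti-fibrotic therapy at baseline.

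The affected outputs are descriptive. No subgroup test or interaction is planned, and anti-fibrotic use is not a term in the primary model of SAP 4.11.2, so the primary test does not change. SAP 4.9 says only that such summaries may be presented, while 4.11.1.6 says that they will be.

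The number of patients affected is probably small. That is a judgement from the eligibility and recording rules, not a figure from the documents. The conclusion on the definition rests only on the SAP 4.9 date rules. The concern about a mixed treatment contrast further assumes that an anti-fibrotic can change cough frequency within the study, which the documents do not address.

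A reader might also infer that a baseline definition removes that mixing. It does not. A baseline user who stops midway stays in the subgroup, and a later starter moves to the non-user group with the same problem. Hence the second part of the fix.

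**What to change.** In SAP 4.9, replace the definition with the following content:

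1. Members are patients with an anti-fibrotic ongoing at study baseline: start date before the first Period 1 dose, and not stopped by that dose.
2. Drugs are identified by a list of WHODD preferred terms and recorded start and stop dates. The medical monitor confirms the list while blinded.
3. Membership is frozen at the blinded data review meeting that SAP 4.4.2 already schedules before database lock and unblinding.
4. Patients who start or stop an anti-fibrotic between the first Period 1 dose and the Period 2 Day 22 recording keep their baseline class, are flagged in the listing, and are left out of a repeat of the subgroup summaries.

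Separately, the placebo rule in the same section should be checked and its anchor changed to first placebo intake if that was meant. The new subgroup would no longer depend on that rule, but the concomitant medication table does.

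The cost is a few sentences, one derived flag and one repeat of the daytime, 24-hour and nighttime summaries. Dates and drug coding are already collected, so no new data are needed.

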4.10 Treatment Exposure / Compliance

Treatment Exposure and Compliance summaries and analyses will be based upon the Safety Set as defined in Section 4.5.

4.10.1 Treatment Exposure

Extent of exposure will be calculated in days and will be derived separately in the two treatment periods according to treatment received.

Extent of exposure in treatment period (days) = Treatment Period last IMP intake - Treatment Period first IMP intake +1

Extent of exposure will be listed by subject and summarized based on Safety analysis set as defined in SAP sections 4.2.4 and 4.2.5.

4.10.2 Compliance

Compliance is defined as the amount of investigational product that should have been taken by a

subject based on the dosing instructions provided during the period for which investigational

product was dispensed.

Compliance, expressed as percent (%), is derived at eCRF level based on the number of tablets actually taken in a particular time interval divided by the number of tablets that should have been taken in that time interval.

Compliance will be assessed at each study visit (on-site or phone visit) via the comparison of reported as not taken or returned blister cards with subject dosing information. The amount of investigational product dispensed and reported as not taken/returned by the subject will be recorded on the drug accountability form at each visit.

Drug accountability variables include:

- Kit Number
- Date Kit Dispensed
- Number of Tablets Dispensed
- Date Kit Returned/ phone visit with reported not-taken kits
- Number of Tablets Returned/Not taken
- Missed doses (Yes/No)
- Number of Tablets Subject was expected to take since last visit
- Number of Tablets Subject actually took since last visit
- Visit Compliance (%) (derived in CRF)

At a visit, each subject compliance status will be classified as follow:

- Compliance < 80%
- Compliance between 80% and 120% (inclusive)
- Compliance > 120%

Drug accountability variables will be listed by subject based on Safety analysis set as defined in SAP section 4.2.4.

Based on Safety analysis set, compliance will be summarized as a continuous variable set as defined in SAP section 4.2.5; as well, compliance status will be summarized as a categorical variable.

4.11 Efficacy Evaluation

All efficacy summaries and analyses will be based upon the FAS as defined in Section 4.5, unless otherwise specified.

4.11.1 Analysis and Data Conventions

4.11.1.1 Multi-center Studies

This is a multicenter, multi-country study.

The statistical model used for assessment of primary endpoint will adjust for site effect.

4.11.1.2 Adjustments for Covariates

The primary efficacy analysis will be adjusted for the following covariates:

- 1. Subject (random repeated effect)
- 2. Study baseline measure of primary efficacy variable
- 4.11.1.3 Handling of Dropouts or Missing Data

Missing or dropout data will not be imputed for the purpose of data analysis.

The Primary Efficacy Analysis will be performed on the FAS and on Completers Analysis Set as sensitivity analysis; there will not be imputation of primary or secondary efficacy endpoints eventually missing at a specific timepoint.

Rules to handle with AEs partial onset and dates will be detailed in section 4.11.1.

4.11.1.4 Multiple Comparisons/Multiplicity

One primary variable has been defined for this study, one critical treatment contrast [NAL-ER vs. Placebo] and one time point of primary interest [Day 22].

Based on the Interim Analysis (IA) look (refer to this SAP at section 4.11.1.5), the study has been interrupted with no sample size adjustment. No alpha adjustment for multiplicity is introduced.

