11.1 Sample Size and Power

The planned sample size of 44 subjects for the final analysis (22 per sequence) provides at least 80% power to detect a 40% reduction in Day 22 daytime cough frequency (coughs per hour) with NAL ER tablet treatment compared to placebo tablets at the 5% significance level (2-sided). This assumes a CV of 1.00 in log-transformed Day 22 cough frequencies. The CV estimated from *Kelsall et al (2011)* data on chronic cough in patients without esophageal catheterization is 1.12; because Kelsall et al data was on 24-hour cough (including nighttime cough, a period of lower coughing rate) and were not taken in a sample of IPF patients only, it is believed that the CV will be lower than in Kelsall et al data. If the CV is larger than planned at 1.25, this sample size provides > 80% power to detect a 50% reduction from placebo to NAL ER. Alternatively, if the CV is 0.75, this sample size provides > 80% power to detect a 34% reduction from placebo to NAL ER.

A total of approximately 60 subjects will be randomized to ensure complete data from at least 44 subjects, assuming up to potentially a 26% dropout rate.

A statistical update on this Proof-of-Concept (POC) study may be conducted when a minimum of 12 subjects have completed both study periods for the purposes of determining whether POC can be established prior to complete enrollment of the study.

The analysis will be based on conditional power (CP). Futility will be declared if the CP is < 10%, while efficacy will be declared if the CP > 80% (*Mehta and Pocock, 2010*). If the CP is at least 41%, the number of subjects per treatment arm may be changed to recover the targeted power of 80%. If it is evident that the outcome is influenced by a baseline imbalance in disease characteristics then the baseline imbalance will be taken into account in supplemental analyses.

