4.5.2 Full Analysis Set

The Full Analysis Set (FAS) will consist of all randomized subjects who have taken at least one dose of study medication and provided study baseline and at least one post-baseline primary efficacy variable assessment during the treatment period. The FAS will be used for the primary efficacy analyses.

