4.11.1.5 Interim Analyses

An interim Analysis has been introduced with Study Protocol, Version 7.0 (December 14, 2021). Purpose of the IA was to have an early look into selected efficacy results in an unblinded fashion. Safety results were not part of the IA.

The Conditional Power method was employed to assess study early futility or efficacy.

Based on the IA results, TREVI took decision not to proceed further with this proof of efficacy study. No sample size re assessment has been considered based on IA results.

IA unblinded results were not disclosed to the main blinded team (including Project Leader, Data Management, Biostatistician and Statistical Programmers).

IA unblinded results were visible only to:

- PAREXEL separate unblinded team (including unblinded Biostatistician and unblinded Statistical Programmers);
- TREVI designated unblinded representative.

Strategy to prevent unauthorized disclosure of unblinded information are detailed in the Blinding Maintenance Plan.

| Trevi Therapeutics, Inc. | |
|--------------------------|---------------------------|
| TR12 | Statistical Analysis Plan |
| | |

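### The interim rule lets efficacy be declared at conditional power above 80% from as few as 12 of 44 completers, and neither the rule nor the final test is adjusted for the look

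*SAP*

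**What the plan says.** Protocol 11.1 plans 44 completers, at least 80% power and a two-sided 5% test. It adds a statistical update that "may be conducted when a minimum of 12 subjects have completed both study periods", based on CP: "Futility will be declared if the CP is < 10%, while efficacy will be declared if the CP > 80" per cent. A third zone, CP of at least 41%, means that "the number of subjects per treatment arm may be changed to recover the targeted power of 80" per cent. The protocol gives no alpha spending, no adjusted final level and no effect size under which CP is calculated.

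SAP 4.11.1.5 confirms that an unblinded efficacy look took place: "The Conditional Power method was employed to assess study early futility or efficacy". It then says the sponsor "took decision not to proceed further with this proof of efficacy study". SAP 4.15 records that recruitment ended after the look, with the last subjects randomized on or before 11 March 2022.

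SAP 4.11.1.4 gives its grounds: one primary variable, one contrast, one time point, and a study interrupted after the look without a sample-size change. It concludes: "No alpha adjustment for multiplicity is introduced". SAP 4.2.5 keeps intervals at the two-sided 0.05 level, and SAP 4.11.2 reports an unadjusted p-value and 95% interval for the geometric mean ratio. SAP 4.5.2 changes the primary population: "The FAS will be used for the primary efficacy analyses".

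**The concern.** Having one variable, one contrast and one time point rules out multiplicity across endpoints. Leaving the sample size alone rules out one adaptive route to inflation. Neither ground addresses testing the same hypothesis at two times with permission to stop at the first.

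CP above 80% is a forecast of final success and need not be strong evidence. Early in a trial a modest result can produce a high forecast if the observed trend, or the design effect, is assumed to continue. At stake is whether the 5% level in protocol 11.1 still describes the p-value and interval that will be reported. A reader cannot settle this, because the documents omit the CP definition, the number in the look, whether futility was binding, how many subjects completed afterwards, and which zone was met.

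**Working it through.** **The plan's own figure.** On the log scale a 40% reduction is −ln(0.60) = 0.5108. CV 1.00 gives a within-subject SD of √ln(1 + 1²) = 0.8326. With 44 crossover completers the standard error is 0.8326 × √(2/44) = 0.1775. Power is Φ(0.5108/0.1775 − 1.96) = 82.1% (80.3% with noncentral t, 42 df). The stated figure of at least 80% reproduces.

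**Set-up.** Let t = n/44, where n is the completers at the look, and let Z1 be the interim statistic, positive for benefit. Under the null hypothesis Z1 and the final Z are bivariate normal with correlation √t. For drift θ (the expected final Z),

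CP = Φ{[√t·Z1 + θ(1 − t) − 1.96] / √(1 − t)}.

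Under current trend θ = Z1/√t, so the limits are:

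- CP 80%: u = √t [1.96 + 0.8416 √(1 − t)]
- CP 10%: l = √t [1.96 − 1.2816 √(1 − t)]

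At n = 12, t = 0.273, √t = 0.522 and √(1 − t) = 0.853. Then u = 0.522 × (1.96 + 0.718) = 1.398 and l = 0.522 × (1.96 − 1.093) = 0.453. Thus Z1 above 1.398, a two-sided p of about 0.16, is enough to declare efficacy, and P(Z1 > 1.398) = 8.1%.

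For a fixed drift, u = [1.96 + 0.8416 √(1 − t) − θ(1 − t)]/√t. The design effect is θ = 1.96 + 0.8416 = 2.80.

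The number in the look is not stated. The protocol minimum of 12 and larger looks up to 26 are shown.

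**Reading A: CP above 80% is the claim.** Benefit-side error = P(Z1 > u) + P(l ≤ Z1 ≤ u, Z44 > 1.96). With futility ignored, the lower limit l is dropped.

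| n at look | u, current trend | Current trend, futility applied | Current trend, futility ignored | Design effect, futility ignored |
|---|---|---|---|---|
| 12 | 1.398 | 9.1% | 9.6% | 12.3% |
| 18 | 1.667 | 5.9% | 6.2% | 8.1% |
| 22 | 1.807 | 4.7% | 5.0% | 6.4% |
| 26 | 1.920 | 4.0% | 4.2% | 5.1% |

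Other fixed drifts behave differently over looks of 12 to 26:

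- Null drift: 2.5% with futility ignored, 0.8% to 1.7% with it applied.
- Drift 1.0: 2.5% to 2.6% ignored, 2.2% to 2.3% applied.
- Drift 1.4 (half the design drift): 2.5% to 2.7% ignored, 2.4% to 2.6% applied.

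**Reading B: the CP limits only stop enrolment, and the accrued data are then tested at 0.05.** With m completers in the end, error = P(Z1 > u or Z1 < l, Zm > 1.96) + P(l ≤ Z1 ≤ u, Z44 > 1.96), under current trend. With futility ignored, only Z1 > u stops enrolment.

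| Look + later completers | Error, futility applied | Error, futility ignored | Two-sided threshold restoring 2.5% (applied / ignored) |
|---|---|---|---|
| 12 + 0 | 3.5% | 4.0% | 0.036 / 0.032 |
| 12 + 10 | 2.8% | 3.1% | 0.045 / 0.040 |
| 12 + 20 | 2.6% | 2.7% | 0.049 / 0.046 |
| 26 + 0 | 3.7% | 3.9% | 0.035 / 0.033 |
| 26 + 10 | 2.6% | 2.8% | 0.048 / 0.045 |
| total 44 | 2.5% | 2.5% | 0.050 / 0.050 |

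**Reading C: a stop for futility only, then a test at 0.05.** The error is 2.0% at 12 + 0, 2.3% at 26 + 0 and 2.5% at a total of 44, so there is no inflation.

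**The case against.** The strongest defence is that the SAP never claims efficacy from the look. It analyses the accrued data in a final model, so the 9% to 12% figures describe a rule that its final test does not use. The protocol gives the look the purpose of judging proof of concept, and the trial is early phase. Some overrun is also likely: two treatment periods and two washouts take about 3 + 2 + 3 + 2 = 10 weeks, so subjects were probably still in progress. On that reading the excess is a few tenths of a percentage point. On a two-sided count with futility applied, even reading A falls below 5% from a look at 22 completers (4.7%), because the futility rule removes almost all rejections in the harmful direction.

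Most of this stands, and it makes reading B the more likely description of the final analysis. It does not remove the problem. Nothing in the SAP withdraws the protocol's declaration rule, and a p-value against a 5% level is still to be reported.

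Two stronger conclusions might be inferred, and neither is supported. The first is that the trial stopped for efficacy and its final p-value is therefore inflated. SAP 4.11.1.5 reports only a sponsor decision not to continue. It does not say the results were favourable or that a CP limit triggered the stop. The second is that only CP under null drift would hold the level. The small fixed drifts above also hold it, or come very close.

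**Conclusion.** As written, the efficacy rule does not hold the benefit-side 2.5% under the two usual definitions of CP. Under current trend the error is 9.1% to 9.6% at 12 completers and 4.0% to 4.2% at 26; under the design effect it is 12.3% and 5.1%. If the look only stopped enrolment, the current-trend excess is small and disappears as the total approaches 44. With null or small fixed drift, or a stop for futility alone, there is no material inflation.

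These figures assume a normal statistic, information proportional to completers out of 44 (approximate, since the FAS is now primary), and no use of the sample-size option, which the SAP says was not considered. They are error rates of the rule and do not show that a false claim was made. The effect on this trial's p-value may be nil. The omission itself is certain and should be fixed.

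**What to change.** Before general unblinding, replace the no-adjustment sentence in SAP 4.11.1.4 with text to this effect:

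> CP above 80% at the interim is not itself a claim of efficacy. The final p-value and 95% interval are either (a) computed with a critical value derived from the stopping rule documented at the time of the look and the actual interim and final information, or (b) if the CP definition or its role in the stop was not documented, labelled nominal and not adjusted for the interim look.

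Option (a) is valid only if the CP rule actually governed the stop. The definition must be the one recorded at the look, not one chosen afterwards. Without that record, (b) applies.

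State the interim number and CP definition in SAP 4.11.1.5. Record the departure from protocol 11.1 in SAP 4.15. Report the limit crossed, if any, and the stopping reason in the clinical study report.

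The cost is wording in three SAP sections and, under (a), one calculation by the existing unblinded team. That critical value depends on the rule and the two sample sizes, so it does not reveal which limit was crossed. The downside is a final threshold at or below 0.05 (0.032 to 0.036 in the extreme case of no overrun, 0.050 at a total of 44), or a p-value described as nominal.
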